## Eligibility Criteria.

Subjects will be eligible to participate if they have a clinical diagnosis of ALS or are a healthy adult; are between 21 and 75 years of age; and have a baseline FVC >60% predicted for age, sex and height. Baseline FVC is routinely performed at every clinic for ALS patients. The AIH study team (PI or coordinator) will email a PFT report request to the clinic respiratory therapist, in advance of clinic. On the day of clinic, the respiratory therapist will upload the requested PFT reports directly into EPIC. After clinic, the AIH study coordinator will locate the PFT report in EPIC and save it to the electronic study binder. If the PFT report indicates the FVC is within study criteria, the subject can be contacted for an appointment. If the FVC falls below study eligibility, the patient will not be scheduled for a screening visit.

Patients will be classified into two groups: 1) uses no form of external respiratory support (IND); and 2) and uses non-invasive external respiratory support while sleeping for at least 2 nights per week to assist night time breathing or treat sleep apnea (NIV). Since 4-6 subjects in each group may fail to meet all eligibility criteria or attend the second testing session, we request to enroll up to 18 patients with ALS, with the goal of completing all study procedures in 12 patients. In addition, we request enrollment of up to 30 healthy controls to complete all study procedures in 20 (up to 20 healthy controls may be needed as a reference set for the EMG data analysis described on *page 10*). The healthy controls will be recruited via listings for this study on CT.gov and the StudyConnect website.

Patient and control participants are ineligible if they: are pregnant, have diagnosed cardiovascular disease, have a BMI >35 kg/m^2, currently take selective serotonin reuptake inhibitors (SSRI), have a history of seizures, have a history of hospitalization for sepsis, had a respiratory infection or took antibiotic medications within the past 4 weeks, use external respiratory support during any waking hours, participate in a pharmaceutical trial to treat ALS, or have any other medical condition the PI ([name]) or medical director ([name]) identify would make it unsuitable to participate.

Additionally, subjects will be ineligible to participate in Aim 3 (caffeine+AIH) if they: report negative side effects to caffeine consumption (e.g. anxiety, dizziness); have a diagnosis of diabetes (due to effect of caffeine on glucose metabolism (55) or hepatic cirrhosis (impaired metabolism of caffeine (56), or take antiarrhythmic or bronchodilator medications (57).

The sample size is consistent with the time and budget required to acquire strong pilot data for an NIH R01 grant, which is the major goal of this project.

Eligible subjects who agree to participate and sign the informed consent form approved by UF will undergo further screening procedures prior to beginning study procedures. Screening will include a detailed medical and pharmacological history, caffeine consumption questionnaire, forced vital capacity (FVC) testing and resting 3-lead ECG. The likelihood of obstructive sleep apnea will be evaluated using the STOP-BANG questionnaire. Subjects will be informed of their STOP-BANG questionnaire results, and if sleep apnea is suspected, then they will be referred for possible clinical treatment (which is outside of the scope of this study). If they choose to pursue clinical treatment for sleep apnea, then they will be included in the study after 3 months of treatment have elapsed. If they choose not to seek treatment, they will be included in the study. This plan is consistent with recommendations of a recent Intermittent Hypoxia workshop considering the inclusion/exclusion of subjects with sleep apnea; recommendations were made in based on input from two nationally known sleep apnea experts participating in that workshop (Drs. [name], University of Chicago, and [name] at Wayne State University).

At the screening session, subjects who meet all study criteria will be invited to participate in a third study session consisting of caffeine + AIH. Subjects who decline to participate in Aim 3 remain eligible to participate in Aims 1-2.

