The dose of intermittent hypoxia is critical in determining the direction and extent of plasticity, and the potential for adverse events (8). For example, high doses of intermittent hypoxia simulating obstructive sleep apnea [80 or more episodes per day/night; severe hypoxemia within each episode] elicit pathology, including systemic hypertension, neuroinflammation, and cognitive impairment (23, 24). On the other hand, respiratory motor plasticity is undermined by severe intermittent hypoxia protocols due to neuroinflammation (25). **In striking contrast**, repeated, low dose AIH [<15 episodes per day; modest hypoxemia per episode] elicits neuroplasticity without detectable pathology (26-31). To the contrary, repetitive low dose AIH exerts beneficial effects in multiple organ systems by independent research groups (for review see: (8)).

Here, we propose to study mechanisms of respiratory plasticity associated with a single presentation of mild AIH. AIH is simple to apply and well tolerated by most individuals. In eight studies on humans with chronic spinal cord injury published to date, an AIH protocol similar to that proposed here has not been associated with any adverse events (5, 7, 31-35). Several other completed, but not yet published studies from multiple laboratories increase our collective experience with (and confidence in) this protocol (Christensen et al., submitted; Sandhu et al., in preparation; Ahmed et al., in preparation). All available evidence is consistent with the conclusion that AIH protocols similar to that proposed here are safe in humans, although we do not yet have experience with ALS

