#### **Screening Tests**

- Forced vital capacity the maximal volume of gas that can be forcefully exhaled, following full inspiration. FVC is a standard measure for clinical care and research, but lacks sensitivity in mild neuromuscular diseases, including ALS (58). Upright FVC will be conducted as per published American Thoracic Society and European Respiratory Society (ATS/ERS) guidelines (59-61). Study team will conduct FVC testing on screening/study visit #1 when any of the following conditions are present: (1) the most recent VC is <63% predicted, (2) most recent VC is >30 days from screening, or (3) written verification of the clinic VC is unavailable. Individuals with an FVC <60% of predicted will be ineligible for further participation in this study.

- 3-lead EKG cardiac rate and rhythm will be evaluated. The presence of resting tachycardia (HR>110 bpm), atrial fibrillation or other dysrhythmias will exclude

subjects from participation.

- Sleep apnea screening. Subjects
  - STOP-BANG questionnaire a validated screening tool for OSA (62). All subjects must complete the STOP-BANG questionnaire, which consists of 4 yes-no questions regarding the presence of symptoms of OSA, plus 4 questions regarding known physical risk factors for obstructive sleep apnea. Individuals who present with a high risk for OSA and are currently not receiving treatment (e.g. overnight positive pressure ventilation or mouthpiece) will be referred to a clinical sleep specialist for further evaluation.
  - Overnight sleep monitor subjects will have the option to wear an overnight sensor that non-invasively monitors arterial oximetry and actigraphy (WatchPAT, Itamar Medical), to estimate the severity of sleep-disordered breathing. Home-based peripheral arterial tonometry has a high specificity/sensitivity for detecting OSA (63). If clinically-significant OSA is detected by the sleep monitor (an apneahypopnea index >10 events/hour), subjects will be referred to a clinical sleep specialist for further evaluation.
  - Caffeine consumption questionnaire- subjects will be asked about their usual daily caffeine consumption habits. We will also ask the subjects about their possible reactions after consuming caffeine. This questionnaire will help us understand the responsiveness of the subjects to caffeine and help rule out individuals with adverse reactions to caffeine.

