# Aim 2 Dependent Variables – Resting/automatic respiratory motor function

- Minute ventilation the pneumotachograph and pressure transducer connected to the face mask will record breath-by-breath flow, volume, mouth pressure, and breathing rate. After achieving a stable tidal volume, 5 minutes of tidal breathing will be recorded. Tidal breathing will be measured at baseline, during hypoxic episodes, immediately following AIH, and at 30 and 60 minutes post-intervention.
- Ventilatory drive. Respiratory drive will be estimated with pressure generation against a transiently occluded airway in the first 0.1 sec of inspiration (ie. P0.1); subjects will

be seated upright and breathing quietly through the face mask. An inspiratory valve will be manually occluded during the expiratory phase of a breath and will be maintained until the end of the subsequent inspiratory effort. Five measurements will be conducted, with 5-15 un-occluded breaths between each  $P_{0.1}$  measurement. This validated test is resistant to learning or sensory bias and reflects unaltered neuromuscular effort (68, 69).  $P_{0.1}$  will be measured at baseline, 30 and 60 minutes post-intervention.

Respiratory muscle EMG. Surface EMGs of the respiratory muscles (up to six muscles, bilaterally: scalene, sternocleidomastoid, 2nd parasternal, 5th external intercostal, 8th external intercostal, and diaphragm) will be recorded during the test session. The root mean square (RMS) of each muscle will be averaged. Multi-muscle activation will be calculated using a validated, vector-based analysis(70) that provides a magnitude (Response Vector) and pattern (Similarity Index) of composite EMG activity. We will then compare multi-muscle activity from each ALS subject to the Prototype Response Vector calculated as the average Response Vector and Similarity Index calculated from the pooled control subjects (71).

Aim 3 Dependent Variables

- Maximal respiratory pressures as described in Aim 1
- Maximal voluntary handgrip force as described in Aim 1
- Tidal breathing pattern as described in Aim 2

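### Healthy controls enter under the patients' FVC floor and with suspected untreated sleep apnea allowed, yet their pooled EMG defines the normal pattern for Aim 2c

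*Combined protocol and SAP*

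**What the plan says.** All references are to the combined protocol and SAP.

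- **One entry rule.** Eligibility Criteria opens with "Subjects will be eligible to participate if they have a clinical diagnosis of ALS or are a healthy adult" and goes on to require that they "have a baseline FVC >60% predicted for age, sex and height". Screening Tests repeats the floor without separating the groups: "Individuals with an FVC <60% of predicted will be ineligible for further participation in this study".
- **One exclusion list.** It begins "Patient and control participants are ineligible if they: are pregnant, have diagnosed cardiovascular disease". It names recent respiratory infection and respiratory support while awake, but not chronic lung disease or sleep apnea.
- **Sleep apnea.** Every subject completes STOP-BANG. Those with suspected apnea are referred. Those who take up treatment wait three months before inclusion. For the others: "If they choose not to seek treatment, they will be included in the study". The objective check is voluntary ("subjects will have the option to wear an overnight sensor"), and an apnea-hypopnea index above 10 events/hour leads to referral only.
- **Use of the controls.** In the Aim 2 dependent variables, each ALS subject's multi-muscle EMG is compared with a prototype "calculated from the pooled control subjects". Eligibility Criteria gives this reference set as the reason for up to 20 completing controls. Controls are also one level of the group factor in the ANOVAs under Statistical Analysis.

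**The concern.** Aim 2c asks whether AIH moves recruitment in ALS back toward normal. The pooled controls define normal, so the answer can be no better than they are. A floor of 60% predicted is a sensible lower limit for a patient group with respiratory weakness. As the only lung-function requirement for a normal reference it is loose, because it admits a control at 61-79% of predicted. The sleep-apnea rule likewise admits controls whose breathing during sleep is suspected to be abnormal and has not been tested.

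At stake are the meaning of the Response Vector and Similarity Index comparison and, to a lesser degree, the patient-versus-control terms in the ANOVAs. The comparison of AIH with sham within patients does not use control data and is not at stake.

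**Working it through.** The plan states no power, effect size, standard deviation or prevalence, so there is no figure of its own to reproduce. The check is a reading of the text followed by illustrations on stated assumptions.

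**1. Is there a control-specific respiratory limit anywhere?** Four provisions might serve as one:

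- The words healthy adult (Eligibility Criteria) have no respiratory definition.
- Exclusion at the discretion of the PI or medical director has no threshold.
- Medical history, the BMI limit of 35 kg/m², and the cardiovascular, rhythm and infection exclusions do not test lung volume or sleep-disordered breathing.
- Baseline FVC as a covariate (Statistical Analysis) is specified only for the EMG outcomes. It adjusts the model but does not change which controls form the prototype, and it does not address sleep apnea.

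None of the four sets a limit.

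**2. How loose is the 60% floor for a control?** Assume healthy FVC has mean 100% of predicted and SD 10-15%.

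- 5th percentile = 100 − 1.645 × SD, which is 84% (SD 10) or 75% (SD 15).
- Distance of the floor = (60 − 100)/SD, which is −4.0 or −2.7 SD.
- Share below 80% = Φ(−20/SD), which is 2.3% or 9.1%. Times 20 controls, this gives about 0.5 to 1.8 people.

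The floor removes almost nobody, but only about 0-2 of 20 controls would be expected below 80%.

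**3. How many controls, and what weight?** Each weighs 1/20 = 5%. For an assumed share p with abnormal breathing, the expected number is 20p and the chance of at least one is 1 − (1 − p)^20:

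| p | expected of 20 | chance of at least one |
|---|---|---|
| 5% | 1 | 64% |
| 10% | 2 | 88% |
| 20% | 4 | 99% |

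For sleep apnea alone, an assumed 10-25% at high risk and untreated gives 2-5 controls, or 10-25% of the prototype.

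**4. Which way would the group comparison move?** Let the mean AIH response be P in patients, C in unaffected controls and A in affected controls. The observed difference is

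P − [(1 − p)C + pA] = (P − C) + p(C − A).

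If affected controls respond less (A < C), the added term is positive. It shrinks the gap when patients respond less than controls and widens it when they respond more. The protocol's rodent section reports facilitation in end-stage ALS rats nearly double that of wild-type littermates, so the second case is plausible. The sign is not known.

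**5. A bound in the diluting direction only.** Suppose affected controls resemble patients fully (A = P). The difference then shrinks by the factor (1 − p). With 12 patients, 20 controls, an assumed true standardized difference of 1.0 and two-sided alpha 0.05, power ≈ Φ[(1 − p)/√(1/12 + 1/20) − 1.96]. This is 78% at p = 0, 69% at p = 10% and 59% at p = 20%. It is a worst case in one direction and not an estimate.

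**The case against.** The case for leaving the criteria alone has real weight.

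- **The sleep-apnea rule is deliberate.** The protocol attributes it to an intermittent-hypoxia workshop with expert input. This stands as a reason for including such subjects. As described, it does not address using them as the normal reference.
- **Symmetric eligibility protects the group comparison.** Patients with suspected untreated apnea are also admitted, and the NIV group may include patients treated for apnea. Excluding high-risk subjects from the controls alone could let a patient-control difference reflect apnea rather than ALS. This stands, and it argues against a control-only STOP-BANG exclusion.
- **The controls are not unselected.** A reader might infer that they are pooled with no selection beyond FVC. That is not so: they must be healthy adults, are age- and sex-matched, and pass the shared exclusions. None of these is a respiratory threshold.
- **The Background does not show that suspected apnea changes a control's response.** It says that "respiratory motor plasticity is undermined by severe intermittent hypoxia protocols due to neuroinflammation", and a reader might carry this over to any control with a positive questionnaire. The passage concerns severe protocols, and it describes apnea-type exposure as 80 or more episodes with severe hypoxemia. Half the STOP-BANG items are physical risk factors, so suspected apnea is not severe apnea. Nor do the documents show that an FVC of 61-79% alters recruitment in an awake, upright subject.
- **The scope is narrow.** The Abstract calls Aim 2 exploratory, and the study is a pilot for a grant application. This limits the importance of the point, but a pilot reference set still has to represent what it is called.

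**Conclusion.** The point holds for the reference set. The text lets people with below-normal FVC or suspected untreated sleep apnea enter the pool that defines normal recruitment in Aim 2c, and no other provision sets a respiratory limit for that pool. It is worth correcting but does not undermine the trial.

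The size is uncertain. Each such control carries 5% of the prototype. The ranges of 2-5 of 20 for suspected apnea and 0-2 of 20 for low FVC rest on assumptions, and the true numbers could be smaller, including none.

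A reader might infer that such controls would hide a patient-control difference in the AIH response. The documents do not support a direction. If patients respond more than controls, as the rodent data suggest they may, blunted controls would widen the gap. Nor do the documents establish that any enrolled control is affected. The within-patient AIH-versus-sham contrast stands as planned.

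**What to change.** 1. In Eligibility Criteria, keep the FVC limit for ALS patients as written. Require controls in the EMG reference set to have FVC in the normal range: at or above the lower limit of normal, or at least 80% predicted. Name one of the two in advance.
2. Keep the sleep-apnea rule for both groups, so that eligibility on that point stays symmetric.
3. In Statistical Analysis, prespecify a sensitivity analysis that rebuilds the prototype and repeats the group comparison. It should leave out controls with a high-risk STOP-BANG result who are untreated and in whom apnea has not been ruled out. It should also leave out any already enrolled control with below-normal FVC. Report it beside the main result.

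**Cost.** FVC and STOP-BANG are already screening items, so no new measurement is needed. A few more controls may fail screening, with 30 − 20 = 10 places to spare. The reference set in the sensitivity analysis would be somewhat smaller. Leaving out 2-5 of 20 leaves 18-15, so the standard error of a prototype mean rises by a factor of √(20/18) = 1.05 to √(20/15) = 1.15 if the spread is unchanged.

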#### **Screening Tests**

- Forced vital capacity the maximal volume of gas that can be forcefully exhaled, following full inspiration. FVC is a standard measure for clinical care and research, but lacks sensitivity in mild neuromuscular diseases, including ALS (58). Upright FVC will be conducted as per published American Thoracic Society and European Respiratory Society (ATS/ERS) guidelines (59-61). Study team will conduct FVC testing on screening/study visit #1 when any of the following conditions are present: (1) the most recent VC is <63% predicted, (2) most recent VC is >30 days from screening, or (3) written verification of the clinic VC is unavailable. Individuals with an FVC <60% of predicted will be ineligible for further participation in this study.

- 3-lead EKG cardiac rate and rhythm will be evaluated. The presence of resting tachycardia (HR>110 bpm), atrial fibrillation or other dysrhythmias will exclude

subjects from participation.

- Sleep apnea screening. Subjects
  - STOP-BANG questionnaire a validated screening tool for OSA (62). All subjects must complete the STOP-BANG questionnaire, which consists of 4 yes-no questions regarding the presence of symptoms of OSA, plus 4 questions regarding known physical risk factors for obstructive sleep apnea. Individuals who present with a high risk for OSA and are currently not receiving treatment (e.g. overnight positive pressure ventilation or mouthpiece) will be referred to a clinical sleep specialist for further evaluation.
  - Overnight sleep monitor subjects will have the option to wear an overnight sensor that non-invasively monitors arterial oximetry and actigraphy (WatchPAT, Itamar Medical), to estimate the severity of sleep-disordered breathing. Home-based peripheral arterial tonometry has a high specificity/sensitivity for detecting OSA (63). If clinically-significant OSA is detected by the sleep monitor (an apneahypopnea index >10 events/hour), subjects will be referred to a clinical sleep specialist for further evaluation.
  - Caffeine consumption questionnaire- subjects will be asked about their usual daily caffeine consumption habits. We will also ask the subjects about their possible reactions after consuming caffeine. This questionnaire will help us understand the responsiveness of the subjects to caffeine and help rule out individuals with adverse reactions to caffeine.

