## **Research Plan**

Figure 1: Proposed screening procedures.

**Design:** Subjects will be screened for eligibility on Day 1 (**Figure 1**); those who meet the criteria will continue with the study.

The study design (**Figure 2**) will consist of up to three separate testing sessions, separated by approximately two weeks (+/- 3 days). One session will be a single, ~45-minute AIH protocol. The other will be 45 minutes of Sham AIH (ie. normoxia). Session order will be random. A third, optional session will be offered to eligible subjects (caffeine + AIH). Each session is expected to last ~3 hours, including equipment setup, patient positioning and pressure relief, rest breaks, AIH/Sham AIH, and post-intervention tests.

Subjects who elect to participate in Aim 3 will be scheduled for a third study session consisting of administration of 3 mg/kg of caffeine, followed by AIH 1 hour after caffeine consumption.

Study outcomes in Aim 1 include strength tests (respiratory and handgrip; MIP and MHGF), respiratory drive (P0.1), tidal breathing, and the hypoxic ventilatory response (HVR). In Aim 2, respiratory muscle recruitment will be tested at normoxic rest, during hypoxia, and with maximal voluntary inspiratory pressure generation. Aim 3 outcomes include maximal respiratory pressures, MHGF, tidal breathing, and saliva tests of caffeine metabolism.

Fig 2 Proposed study design.

**Subjects:** We propose to study 18 ALS patients and up to 30 healthy age/sex matched control subjects. Patients who meet study criteria will be identified by [name] (Co-I) through the UF adult neuromuscular clinic. The study PI will screen and consent patients. The PI will review the eligibility criteria. study procedures, participation risks, and the ability of subjects to withdraw from the study at any time.

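### The 30-day limit on vital capacity age is counted to screening, so a participant deferred for sleep-apnea treatment can reach the first session on an FVC about 91 to 121 days old

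*Combined protocol and SAP*

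**What the plan says.** The entry criterion under Eligibility Criteria is that participants "have a baseline FVC >60% predicted for age, sex and height". Screening Tests repeats it as an exclusion: "Individuals with an FVC <60% of predicted will be ineligible for further participation in this study".

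For patients, the value normally comes from the clinic: "Baseline FVC is routinely performed at every clinic for ALS patients". According to Screening Tests, the study team does its own test, at the screening or first study visit, in three cases: "the most recent VC is <63% predicted"; "most recent VC is >30 days from screening"; or the clinic value cannot be confirmed in writing. Otherwise the clinic value stands.

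The Research Plan states: "Subjects will be screened for eligibility on Day 1". The list of procedures after consent begins "Screening will include a detailed medical and pharmacological history" and goes on to FVC and a 3-lead ECG; the next sentence adds the STOP-BANG questionnaire. If apnea is suspected and the participant takes up treatment, "then they will be included in the study after 3 months of treatment have elapsed". A participant who declines treatment enters with no set wait.

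The Statistical Analysis section uses baseline FVC as a covariate for the surface EMG Response Vector and Similarity Index, and gives no date window for it. FVC is not among the session measurements listed as dependent variables for Aims 1 to 3.

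**The concern.** The plan treats a clinic value 31 days old at screening as too old to rely on. Its own apnea branch then places at least three months between that screening and the first session, and the age rule does not reach across the gap. A value that was current at screening stays valid under the rule however long the deferral lasts.

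Two uses of FVC are touched. It is the respiratory floor for breathing 9 to 12% oxygen, and for a deferred ALS patient that floor would not be confirmed near the first exposure. It is also the covariate in the EMG comparison of patients with controls. If FVC falls during the wait, the recorded value overstates FVC at testing. That would be expected mainly in patients, since healthy controls have no progressive loss.

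**Working it through.** There is no stated figure to reproduce, so the check is a timeline.

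**Inputs from the documents**
- Age of an accepted clinic VC at screening: 0 to 30 days (Screening Tests).
- Treatment period before entry: 3 months (Eligibility Criteria).
- Gap between sessions: two weeks, plus or minus 3 days, so 11 to 17 days (Research Plan).

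**Assumptions**
- One month is 30.4 days, so 3 months is 3 × 30.4 = 91 days.
- The lag L from screening to the start of treatment is not given. I take 0 days as the minimum and 30 days as an illustration.

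**Formula:** FVC age at session 1 = (age at screening) + L + 91.

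| Case | Session 1 |
|---|---|
| Not deferred, screening and session 1 on the same day | 0 to 30 days |
| Deferred, L = 0 | 0 + 91 = 91 to 30 + 91 = 121 days |
| Deferred, L = 30 (assumed) | 0 + 30 + 91 = 121 to 30 + 30 + 91 = 151 days |

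For later sessions with L = 0:
- Session 2: 91 + 11 = 102 to 121 + 17 = 138 days.
- Optional session 3: 91 + 22 = 113 to 121 + 34 = 155 days.

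Because the order of AIH and Sham is random, the first hypoxic exposure may fall at session 1 or session 2.

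The range of 91 to 121 days is close to a minimum, because the wait is counted in months of treatment, and referral and treatment start come first.

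**With the limit counted to the first session:** at most 30 days at session 1, 30 + 17 = 47 at session 2, and 30 + 34 = 64 at session 3.

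**The case against.** **A second screening may be intended.** Inclusion happens on return, FVC is a condition of inclusion, and the rule refers to the latest VC. A returning participant could therefore be screened afresh, which would restart the clock. A patient who starts overnight positive pressure for apnea would also move from the unsupported group to the non-invasive ventilation group, which points to some reassessment. Figure 1, on screening procedures, is not shown in the copy reviewed. This reading is possible, but no readable text states it. The same section says of those who decline treatment that they will be included, and nothing there suggests a second screening for them; it uses the same expression for those who return.

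**A newer clinic value may exist.** For patients this is plausible, since FVC is done at each clinic visit. But the report-request procedure serves to decide whether to schedule a screening visit, and no rule says to obtain or apply a later value after deferral. The point makes the fix cheap; it does not close the gap.

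**Stronger readings that the documents do not support.** Four inferences are tempting.
- *The gap between the 63% re-test trigger and the 60% floor is an allowance for decline, which the deferral uses up.* The plan gives no reason for the 63% figure, and it may equally cover test-to-test variation. Nor does it fit participants whom the team tests at screening, who can be accepted just above 60%.
- *A given number of patients would fall below the floor.* The documents give neither a rate of FVC decline nor a count of deferred participants.
- *The EMG result would be biased by a known amount.* No relation between FVC and the EMG measures is given. Only one exploratory analysis uses the covariate; the ANOVAs for strength, resting ventilation and respiratory drive do not name it.
- *The gap exposes participants to harm.* Continuous SpO2 monitoring, oxygen titration and the stop limits apply at each AIH session, and harm does not follow from the age of the FVC.

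**Conclusion.** The concern holds as a matter of wording. The 30-day rule is tied to screening, the apnea branch separates screening from testing by at least three months, and nothing readable bridges the two. A first session on an FVC about 91 to 121 days old is permitted, roughly three to four times the plan's own limit (91/30 = 3.0; 121/30 = 4.0). The lower end assumes that treatment starts on the day of screening; a later start adds day for day.

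The practical size is unknown. The route needs suspected and untreated apnea and a decision to seek treatment; if nobody takes it, the effect is nil. What remains is an entry floor, and the date of an exploratory covariate, that can be tied to the right time point at little cost. I would offer it as an optional improvement.

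**What to change.** In Screening Tests, reword the second re-test condition to: *the latest VC was obtained more than 30 days before the first testing session*. Let the study team's test take place at any point up to that session, since the rule now places it at the screening or first study visit. A deferred participant then has either a recent clinic value or a repeat FVC, and must still meet the 60% criterion. In Statistical Analysis, define baseline FVC as that value. The criteria and the session spacing stay as they are. If a second screening is what the plan intends, the reworded condition is consistent with it. Repeating the history and ECG is a separate matter, which the VC-age rule does not call for.

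The cost is one short spirometry per deferred participant without a recent clinic value. The same applies to any other participant whose first session slips beyond the 30 days, because the plan sets no maximum interval between screening and session 1. The real downside is that a deferred patient whose FVC has dropped below 60% would be lost against the target of 12 patients completing.
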